#### **5.5.1.1. Liver Chemistry Stopping Criteria, Participant Management and Follow-Up**

Participants who develop ALT  $\geq 5$ xULN must be followed weekly until resolution or stabilization (ALT  $< 5$ xULN on 2 consecutive evaluations).

#### **When any of the liver chemistry stopping criteria is met, do the following:**

- Immediately hold IP. If on LA therapy, **do not** administer another injection until approval is received from the ViiV Safety and Labelling Committee.
- Report the event to the Medical Monitor within 24 hours of learning its occurrence.
- Complete the liver event eCRF and SAE eCRF, where applicable.
- Complete the liver imaging and/or liver biopsy eCRFs if these tests are performed.
- Perform liver event follow up assessments (described below), and monitor the participant until liver chemistries resolve, stabilize, or return to Baseline values as described below.
- Make every reasonable attempt to have participants return to clinic within 24 hours for repeat liver chemistries, liver event follow-up assessments (see below), and close monitoring.
- A specialist or hepatology consultation is recommended.
- Monitor participants twice weekly until liver chemistries (ALT, AST, alkaline phosphatase, bilirubin) resolve, stabilize or return to within Baseline values.

Make every attempt to carry out the **liver event follow-up assessments** described below:

- Viral hepatitis serology including:
  - Hepatitis A immunoglobulin M (IgM) antibody;
  - Hepatitis B surface antigen (HBsAg) and Hepatitis B Core Antibody (IgM);
  - Hepatitis C RNA;
  - Hepatitis E IgM antibody;
  - Cytomegalovirus IgM antibody;

- Epstein-Barr viral capsid antigen IgM antibody (or if unavailable, obtain heterophile antibody or monospot testing);
- Syphilis screening;
- Drugs of abuse screen including alcohol;
- Serum acetaminophen test (N-acetyl-para-aminophenol [APAP] adduct test). The site must contact GSK when this test is required. Please refer to the central laboratory manual.
- Blood sample for pharmacokinetic (PK) analysis, obtained during follow up assessments. Record the date/time of the PK blood sample draw and the date/time of the last dose of investigational product prior to blood sample draw on the eCRF. If the date or time of the last dose is unclear, provide the participant's best approximation. If the date/time of the last dose cannot be approximated OR a PK sample cannot be collected in the time period indicated above, do not obtain a PK sample. Instructions for sample handling and shipping are in the SPM.
- Serum creatine phosphokinase (CPK) and lactate dehydrogenase (LDH);
- Fractionated bilirubin, if total bilirubin is greater than 1.5xULN;
- Obtain complete blood count with differential to assess eosinophilia;
- Anti-nuclear antibody, anti-smooth muscle antibody, and Type 1 anti-liver kidney microsomal antibodies, and quantitative total immunoglobulin G (IgG or gamma globulins);
- Liver imaging (ultrasound, magnetic resonance, or computerized tomography) and/or liver biopsy to evaluate liver disease; complete Liver Imaging and/or Liver Biopsy CRF forms.
- Record the appearance or worsening of clinical symptoms of hepatitis, or hypersensitivity, fatigue, decreased appetite, nausea, vomiting, abdominal pain, jaundice, fever, or rash as relevant on the AE report form;
- Record use of concomitant medications, acetaminophen, herbal remedies, other over the counter medications, or putative hepatotoxins, on the concomitant medications report form. Record alcohol use on the liver event alcohol intake case report form.

#### **5.5.1.2. Liver Event Adjudication Committee**

A liver safety panel will be used to evaluate all participants who meet liver stopping criteria. Uniform sets of data and standards for adjudication will be applied across cases to inform outcomes. Full details of the analysis, timing, and the decision criteria will be pre-specified in an Adjudication Committee Charter.

#### **5.5.1.3. Liver Chemistry Stopping Criteria – Restart**

Participants who meet liver toxicity stopping criteria should not be retreated with investigational product unless an exemption has been approved by the ViiV Safety and Labeling Committee (VSLC). The guideline for Restart approved by the VSLC, which is maintained as a separate document must be followed.

#### 5.5.1.4. General Guidance Restart

- The definition of ‘restart’ is not always clear cut in medical practice. Restarts should be limited to cases in which there is clear evidence that the underlying cause of the liver event is not related to study drug.
- For long acting agents, a restart may actually be continuation of therapy rather than a true re-start due to the timeframe between dose administration relative to decision making on allowing a restart.
- If protocol defined stopping criteria for liver chemistry elevations are met (see Section 5.5.1), study drug must be stopped. Participants who meet liver chemistry stopping criteria should not be retreated with investigational product unless an exemption has been approved by the VSLC. The guideline for Restart approved by the VSLC, which is maintained as a separate document must be followed.
- If the restart is approved by the VSLC in writing, the participant must be provided with a clear description of the possible benefits and risks of drug administration, including the possibility of recurrent, more severe liver injury or death.
- Ethics Committee or Institutional Review Board approval of drug restart must be obtained, as required.
- The participant must also provide signed informed consent specifically for the IP restart. Documentation of informed consent must be recorded in the study chart.
- Study drug must be administered at the dose specified by the VSLC.
- Participants approved by the VSLC for restart of IP must return to the clinic once a week for liver chemistry tests for a minimum of one month and thereafter for as long as clinically indicated and then laboratory monitoring may resume as per protocol. Longer durations of close monitoring may be required for long acting IP.

##### 5.5.1.4.1. Drug Restart

“Drug restart” can be approved by the VSLC for **defined non-drug-induced** liver injury if no evidence of:

- immunoallergic injury /HLA association with injury
- alcoholic hepatitis

Study drug must be held while labs and evaluation are completed to assess diagnosis.

If participant meets liver chemistry stopping criteria do not restart the participant with study treatment unless:

- ViiV Healthcare Safety and Labelling Committee (VSLC) approval **is granted**,

- Ethics and/or IRB approval is obtained, if required, and
- Separate consent for treatment restart is signed by the participant.

Refer to Section 11.3 for full guidance.

#### Background

- Restarts should be limited to cases in which there is clear evidence that the underlying cause of the liver event is not related to study drug.
- For long-acting agents, a restart may actually be continuation of therapy rather than a true re-start due to the timeframe between dose administration relative to decision making on allowing a restart.
- If protocol defined stopping criteria for liver chemistry elevations are met (Section 11.3), study drug must be stopped. Subjects who meet liver chemistry stopping criteria should not be retreated with investigational product unless an exemption has been approved by the VSLC. The algorithm for restart is described in Section 11.3 and summarised in Figure 8.
- If the restart is approved by the VSLC in writing, the subject must be provided with a clear description of the possible benefits and risks of drug administration, including the possibility of recurrent, more severe liver injury or death.
- Ethics Committee or Institutional Review Board approval of drug restart must be obtained, as required.
- The subject must also provide signed informed consent specifically for the IP restart. Documentation of informed consent must be recorded in the study chart.
- Study drug must be administered at the dose specified by the VSLC.
- Subjects approved by the VSLC for restart of IP must return to the clinic once a week for liver chemistry tests for a minimum of one month and thereafter for as long as clinically indicated and then laboratory monitoring may resume as per protocol. Longer durations of close monitoring may be required for long-acting IP.

Refer to Section 11.3 for full guidance.

#### **5.5.1.4.2. Drug Restart Following Transient Resolving Liver Events Not Related to IP**

Approval by the VSLC for drug restart or additional IM administration can be considered where:

- Abnormalities in liver chemistries have a clear underlying cause (e.g., biliary obstruction, hypotension, acute viral hepatitis) and liver chemistries have significantly improved.
- If definitive non-study drug related diagnosis, restart will be considered once ALT < 3x ULN (for participants with baseline ALT < 1.5x ULN) or < 3x baseline ALT value (for participants with baseline ALT > 1.5x ULN).
- Ethics Committee or Institutional Review Board approval of drug restart must be obtained, as required.
- If restart / redosing of drug is approved by the VSLC in writing, the participant must be provided with a clear description of the possible benefits and risks of drug administration, including the possibility of recurrent, more severe liver injury or death.
- The participant must also provide signed informed consent specifically for the restart. Documentation of informed consent must be recorded in the study chart.

Study drug must be administered at the dose specified by the VSLC. Participants approved by the VSLC for restarting or re-dosing IP must return to the clinic once a week for liver chemistry tests for a minimum of one month and thereafter for as long as clinically indicated and then laboratory monitoring may resume as per protocol. If protocol defined stopping criteria for liver chemistry elevations are met, study drug must be stopped.

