18. Evidence of Hepatitis B virus (HBV) infection based on the results of testing at Screening for Hepatitis B surface antigen (HBsAg), Hepatitis B core antibody (anti-HBc), Hepatitis B surface antibody (anti-HBs) and HBV DNA as follows:
- a. •Participants positive for HBsAg are excluded;
  - b. •Participants negative for anti-HBs but positive for anti-HBc (negative HBsAg status) and positive for HBV DNA are excluded
- Note:* Participants positive for anti-HBc (negative HBsAg status) and positive for anti-HBs (past and/or current evidence) are immune to HBV and are not excluded.
19. Asymptomatic individuals with chronic hepatitis C virus (HCV) infection will not be excluded, however Investigators must carefully assess if therapy specific for HCV infection is required; participants who are anticipated to require HCV treatment within 12 months must be excluded. (HCV treatment on study may be permitted post Week 52, following consultation with the medical monitor)
20. Participants with HCV co-infection will be allowed entry into this study if:
- a. Liver enzymes meet entry criteria
  - b. HCV Disease has undergone appropriate work-up, and is not advanced, and will not require treatment prior to the Week 52 visit. Additional information (where available) on participants with HCV co-infection at screening should include results from any liver biopsy, Fibroscan, ultrasound, or other fibrosis evaluation, history of cirrhosis or other decompensated liver disease, prior treatment, and timing/plan for HCV treatment.
  - c. In the event that recent biopsy or imaging data is not available or inconclusive, the Fib-4 score will be used to verify eligibility
    - i. Fib-4 score >3.25 is exclusionary
    - ii. Fib-4 scores 1.45 – 3.25 requires Medical Monitor consultation

Fibrosis 4 Score Formula:

$$(Age \times AST) / (Platelets \times (\sqrt{ALT}))$$
21. Unstable liver disease (as defined by any of the following: presence of ascites, encephalopathy, coagulopathy, hypoalbuminemia, esophageal or gastric varices, or persistent jaundice or cirrhosis), known biliary abnormalities (with the exception of Gilbert's syndrome or asymptomatic gallstones or otherwise stable chronic liver disease per investigator assessment)
22. History of liver cirrhosis with or without hepatitis viral co-infection.
23. Ongoing or clinically relevant pancreatitis

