31. Any acute laboratory abnormality at Screening, which, in the opinion of the investigator, would preclude the participant's participation in the study of an investigational compound
32. Participant has estimated creatine clearance  $< 50$  mL/min per  $1.73\text{m}^2$  via Chronic Kidney Disease-Epidemiology Collaboration (CKD-EPI) Method
33. Alanine aminotransferase (ALT)  $\geq 3 \times$  ULN

Concomitant Medications

34. Exposure to an experimental drug (with the exception of those in the ATLAS study including CAB, CAB LA, and RPV LA) or experimental vaccine within either 30 days, 5 half-lives of the test agent, or twice the duration of the biological effect of the test agent, whichever is longer, prior to Day 1 of this study;
 
35. Treatment with any of the following agents within 28 days of Screening:
 
 
• radiation therapy;
 
• cytotoxic chemotherapeutic agents;
 
• tuberculosis therapy with the exception of isoniazid (isonicotinylhydrazid, INH);
 
• anti-coagulation agents;
 
• Immunomodulators that alter immune responses such as chronic systemic corticosteroids, interleukins, or interferons. Note: Participants using short-term (e.g. <math>\leq 21</math> days) systemic corticosteroid treatment; topical, inhaled and intranasal corticosteroids are eligible for enrolment.
 
 
36. Treatment with an HIV-1 immunotherapeutic vaccine within 90 days of Screening
 
37. Treatment with any agent, except recognized ART as allowed above, with documented activity against HIV-1 within 28 days of study Day 1. Treatment with acyclovir/valacyclovir is permitted.
 
38. Use of medications which are associated with Torsade de Pointes. (See SPM for a list of relevant medications)
 
39. Current or prior history of etravirine (ETR) use
 
40. Current use of tipranavir/ritonavir or fosamprenavir/ritonavir
 
41. Participants receiving any prohibited medication and who are unwilling or unable to switch to an alternate medication. Note: Any prohibited medications that decrease CAB or RPV concentrations should be discontinued for a minimum of four weeks or a minimum of three half-lives (whichever is longer) prior to the first dose and any other prohibited medications should be discontinued for a minimum of two weeks or a minimum of three half-lives (whichever is longer) prior to the first dose

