### 5.5.1. Liver Chemistry Stopping Criteria

**Liver chemistry stopping and increased monitoring criteria** have been designed to assure participant safety and evaluate liver event etiology.

IP will be stopped if any of the following liver chemistry criteria are met:

- ALT  $\geq 3xULN$  and bilirubin  $\geq 2xULN$  (>35% direct bilirubin, bilirubin fractionation required).
- NOTE: serum bilirubin fractionation should be performed if testing is available. If testing is unavailable, sites should evaluate the presence of detectable urinary bilirubin on dipstick, indicating direct bilirubin elevations and suggesting liver injury. If testing is unavailable and a participant meets the criterion of total bilirubin  $\geq 2xULN$ , then the event meets liver stopping criteria.
- ALT  $\geq 8xULN$ .

- ALT  $\geq 3$ xULN (if Baseline ALT is  $< \text{ULN}$ ) with symptoms or worsening of acute hepatitis or hypersensitivity such as fatigue, nausea, vomiting, right upper quadrant pain or tenderness, fever, rash, or eosinophilia, OR;
- ALT  $\geq 3$ x Baseline ALT with symptoms or worsening of acute hepatitis or hypersensitivity such as fatigue, nausea, vomiting, right upper quadrant pain or tenderness, fever, rash, or eosinophilia;
- ALT  $\geq 5$ xULN and  $< 8$ xULN that persists  $\geq 2$  weeks (with bilirubin  $< 2$  ULN & no signs or symptoms of acute hepatitis or hypersensitivity).
- ALT  $\geq 5$ xULN but  $< 8$ xULN and cannot be monitored weekly for  $> 2$  weeks.

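### For some participants with raised Baseline ALT, the numeric restart condition in Section 5.5.1.4.2 can be met by an ALT that still meets a stopping criterion in Section 5.5.1

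*Protocol*

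**What the plan says.** Section 5.5.1 is an any-of rule: "IP will be stopped if any of the following liver chemistry criteria are met". Three of its criteria matter here:

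- ALT of 8xULN or more, with no further condition.
- ALT of at least 5xULN but below 8xULN lasting 2 weeks or more, with bilirubin below 2xULN and no signs or symptoms of acute hepatitis or hypersensitivity.
- ALT in the same band that "cannot be monitored weekly for" more than 2 weeks.

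None of these three refers to Baseline. A separate criterion does: ALT of at least 3 times Baseline with symptoms.

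Section 5.5.1.4.2 covers restart after a transient liver event not related to study drug. With a definitive non-drug diagnosis, "restart will be considered once ALT < 3x ULN (for participants with baseline ALT < 1.5x ULN"), and for the others the condition is "or < 3x baseline ALT value (for participants with baseline ALT > 1.5x ULN"). It also asks for a clear underlying cause, significantly improved chemistries, written VSLC approval, ethics approval where required and separate consent. Its last sentence reads: "If protocol defined stopping criteria for liver chemistry elevations are met, study drug must be stopped".

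On entry, exclusion criterion 33 in Section 5.2 removes Screening ALT of 3xULN or more, so values up to just under 3xULN are admitted. Criterion 20 also lets in participants with hepatitis C co-infection, subject to conditions.

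**The concern.** The restart ceiling for raised Baseline grows with Baseline, while the 5xULN and 8xULN stops stay fixed. At a high enough Baseline the ceiling must overtake them. One ALT value would then satisfy the numeric restart condition and a stopping criterion together, and Section 5.5.1.4.2 would disagree with its own last sentence.

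This matters because the section expressly covers further intramuscular dosing, and a long-acting injection cannot be taken back once given. A participant redosed in the overlap could meet a stopping criterion at the next weekly liver test. The lower-Baseline branch of the same sentence does not have this problem: its ceiling of 3xULN lies below both limits.

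**Working it through.** The plan gives no figure to reproduce, so the check sets the two rules on one scale.

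**Inputs**

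- b = Baseline ALT in multiples of ULN. The raised-Baseline branch needs b > 1.5 (Section 5.5.1.4.2).
- Upper bound b < 3, from exclusion criterion 33. This assumes that Baseline stays within the Screening limit. A higher Day 1 value would raise the ceiling further.
- Stopping limits of 8xULN (unconditional) and 5 to <8xULN (conditional), from Section 5.5.1.

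**Formula:** restart ceiling = 3b.

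- Range: 3 × 1.5 = 4.5xULN, up to just under 3 × 3 = 9xULN.
- Passes 5xULN when b > 5/3 = 1.67.
- Passes 8xULN when b > 8/3 = 2.67.

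| Baseline (xULN) | Restart if ALT below (xULN) | Above 5xULN? | Above 8xULN? |
|---|---|---|---|
| 1.6 | 4.8 | no | no |
| 1.75 | 5.25 | yes | no |
| 2.0 | 6.0 | yes | no |
| 2.5 | 7.5 | yes | no |
| 2.75 | 8.25 | yes | yes |
| 2.9 | 8.7 | yes | yes |

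**Example against the unconditional stop.** Baseline 2.8xULN gives a ceiling of 3 × 2.8 = 8.4xULN. An ALT that has come down to 8.2xULN is below 8.4, so it meets the restart value. It is also at least 8, so it meets the stop.

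**Example against the persistence stop.** Baseline 2.0xULN gives a ceiling of 6.0xULN. Suppose ALT falls from 7.5 to 5.8xULN over more than 2 weeks, with bilirubin below 2xULN and no symptoms. The fall is 1.7xULN, or 1.7/7.5 = 23%, and could be judged an improvement. The value of 5.8 is below 6.0, so it meets the restart value. ALT has also stayed between 5 and 8xULN for over 2 weeks, so the persistence criterion is still met.

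**How much of the range is involved.** The band from 1.5 to 3xULN is 1.5 wide. The part with a ceiling above 5xULN is (3 − 1.67)/1.5 = 89%, and above 8xULN it is (3 − 2.67)/1.5 = 22%. These are shares of the Baseline range, not of participants. The documents give no distribution of Baseline ALT.

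**The case against.** The strongest reply is that the ALT value does not by itself permit restart. The section is limited to transient, resolving events with a definitive non-drug cause. It requires significant improvement, written VSLC approval and consent, and approval is only something that can be considered. Sections 5.5.1.3 and 5.5.1.4 present retreatment after a stop as an exemption that the VSLC grants. Section 7.4.4.2 also requires consultation with the Medical Monitor at ALT of 3xULN or more before long-acting dosing starts or continues. And a multiple of Baseline is not out of place, since the symptomatic stopping criterion uses one too.

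All of that stands, and it limits the practical risk. It does not remove the conflict. Significant improvement carries no number, and both examples above are compatible with a falling ALT. The closing sentence of Section 5.5.1.4.2 requires a stop without mentioning an exemption. The restart value agrees with the symptomatic criterion but was not aligned with the 5xULN and 8xULN criteria.

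Four stronger readings are tempting, and the documents do not support them:

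- *That the restart value lies above both limits for everyone with raised Baseline.* Up to a Baseline of 1.67xULN it is above neither, and it passes 8xULN only from about 2.67xULN.
- *That any ALT of 5xULN or more requires stopping.* Between 5 and 8xULN the stop depends on persistence or on weekly monitoring being impossible.
- *That restart could follow with no fall in ALT.* The number alone would allow this, but the improvement requirement would not.
- *That restart is allowed while the event is unresolved by the protocol's own definition.* Section 5.5.1.1 says that participants with ALT of 5xULN or more "must be followed weekly until resolution or stabilization", taken as ALT below 5xULN on two consecutive evaluations. That decides when weekly follow-up ends. It is not stated as a condition for restart.

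Finally, Sections 5.5.1.3 and 5.5.1.4.1 point to a separate VSLC guideline and to Section 11.3 for full guidance. Neither was available for checking. If either sets a cap, Section 5.5.1.4.2 does not reflect it and would still need aligning.

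**Conclusion.** The concern holds as a minor reconciliation point. The numeric restart condition for Baseline ALT above 1.5xULN has no absolute cap, with a ceiling of 4.5 to just under 9xULN. It conflicts outright with the 8xULN stop for Baseline of about 2.67 to <3xULN. It conflicts conditionally with the persistence stop for Baseline above about 1.67xULN. It conflicts with neither limit between 1.5 and 1.67xULN.

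This rests on Baseline being bounded by the Screening exclusion. The number of participants affected cannot be derived from the protocol and is likely small. The other gates make it unlikely that the ALT value alone would lead to a restart, so the documents do not show that participants would be redosed in the overlap. They show only that the written number does not prevent it.

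**What to change.** Reconcile Section 5.5.1.4.2 with Section 5.5.1, and both with Section 11.3 and the separate VSLC restart guideline, so that an ALT currently meeting a stopping criterion cannot satisfy the numeric restart condition. If the sponsor intends the VSLC exemption to override a criterion that is still met, the text should say so, and the closing sentence of Section 5.5.1.4.2 should be made consistent with it.

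The threshold is for the sponsor to set, and none is proposed here. In particular, the Section 5.5.1.1 follow-up definition should not be imposed as a restart rule.

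The cost is about one sentence in the protocol, plus a check of Section 11.3 and the guideline and an edit there if needed. No extra tests or visits follow.
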